In contrast to its effect in obstructive sleep apnea, supplemental oxygen in patients with central sleep apnea not only improves oxygenation, but often leads to a reduction in the frequency of apneas and hypopneas, with the reported reduction in AHI typically 40-75% (55-59). Two controlled studies have examined the effect of nocturnal supplemental oxygen on cardiac function (58, 59). These studies showed improvements in LVEF of 5.5-9.7% following 3 to 12 months of treatment, with increases in LVEF of only 1.3% among controls in each study. A third, uncontrolled trial was included with these in the AASM Practice Parameters paper meta-analysis, which estimated the effect of nocturnal supplemental oxygen on LVEF to be 5.0% (41); again, all were small, single-center, unregistered clinical trials, with an average sample

size of only 26.7. Two studies have reported that nocturnal oxygen improves exercise capacity, with increases in maximal oxygen consumption on cardiopulmonary exercise testing of 2.3-5 ml/kg/min (55, 58). Little is known regarding the effect of oxygen treatment for sleep apnea on long-term cardiovascular risk.

(b) Significance

HF is a common disease with high morbidity, mortality and health care utilization. Sleep apnea is highly prevalent in patients with chronic HF and is associated with a doubling of mortality risk, although it is commonly asymptomatic and usually goes undiagnosed. There are currently three approved therapies for sleep apnea in patients with HF, although as noted above ASV will soon be contraindicated in this patient population. The present study will for the first time directly compare the two remaining treatments, evaluating their effects on ventricular function, exercise capacity, and other markers of risk for progression of HF. This study will also lay the foundation for a long-term study comparing the effects on morbidity and mortality of these therapies for treatment of sleep apnea in patients with chronic HF.

(c) Relevance to Veterans Health

Heart failure is reported to be the most common medical discharge diagnosis for veterans treated within the VA system (3). Heart failure also carries a high mortality risk, with 1-year mortality of approximately 20% and 5-year mortality of 42-54%. Sleep apnea is a common co-morbid condition associated with increased HF mortality. Identifying the optimal treatment regimen for sleep apnea in patients with HF is therefore of great relevance to Veterans health.

(3) Work Proposed

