In addition to HLSE, this intervention includes nightly treatment with nocturnal supplemental oxygen (NSO). Oxygen therapy will be initiated at 2 lpm via nasal cannula, with routine clinical follow-up using overnight oximetry to assess adequacy of this flow rate. If needed, oxygen will be increased in 1 lpm increments as needed to (1) maintain baseline saturation >90%, and (2) to reduce the frequency of 3% oxyhemoglobin desaturation events to <5 per hour (independent of baseline saturation level). As oxygen at 2 lpm via nasal cannula has been shown to reduce the number of 4% desaturations during sleep in patients with sleep apnea by 89%, we anticipate that most participants will be adequately treated at 2-4 lpm. Oxygen is provided by a stationery oxygen concentrator. Adherence with oxygen use is measured by hours of machine use over the intervention period.

Interim telephone contact

Following initiation of therapy, study staff will make telephone contact with each participant at weeks 1, 2, 4 and 8 to identify any early problems with treatment adherence and to ascertain any adverse events. In particular, sleepiness will be re-assessed using the Epworth Sleepiness Scale and [name] or [name] will contact any patient whose Epworth Sleepiness Scale score is ≥ 16 or who provides a response of 2 or 3 on the item regarding drowsy driving. At week one the Healthy Lifestyle Education will be presented to each group over the phone in conjunction with education materials set home with patient at baseline visit.

Final study visit

After 12 weeks of intervention, participants will return for a final study visit at which time all procedures performed at the baseline visit will be repeated, including phlebotomy, echocardiography, cardiopulmonary exercise testing, and questionnaire administration. Participants will be asked to complete, while wearing the assigned therapy 24-hour ambulatory blood pressure monitoring.

Following completion of study procedures, each participant will be encouraged to accept referral to a sleep specialist within the VA to discuss treatment of sleep apnea.

Statistical analysis

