This study is a randomized clinical trial with three parallel treatment groups, designed to compare the active treatment groups (CPAP and NSO) to the optimal medical management comparator (HLSE). Baseline data will be summarized using standard descriptive statistics for demographic and baseline clinical characteristics by treatment group. Based on our experience with the HeartBEAT Study, the rate of dropouts during the course of the three-month trial is expected to be low and we do not expect dropouts

to be differential with respect to treatment group assignment. The main analysis will include all subjects completing the follow-up examination. For the purposes of a sensitivity analysis, a result of “no change” will be imputed for all drop-outs, and compared to the main analysis.

The analysis for each of the primary outcome measures (LVEF and peak VO₂) will consist of a one-factor analysis of variance comparing the mean changes from baseline in LVEF (or VO₂). As we postulate similar benefits from CPAP and NSO, we will specify two contrasts: CPAP vs. HLSE and NSO vs. HLSE as our primary analyses. In a secondary analysis, we will also compare the effects of CPAP to NSO for the purpose of hypothesis generation for subsequent larger studies. This analysis is a simple analysis of variance, with data transformation or adoption of rank-based inference if approximate normality is not present. While the randomization should achieve approximate balance on potentially confounding conditions, analysis of covariance models that employ adjustments for recruitment site, age, sex, sleep apnea severity, comorbid illness, smoking and alcohol use will be fit to potentially improve the efficiency of the treatment effect estimates. Should a significant difference between treatment and comparator be identified, further exploratory analyses will assess the relation of adherence to therapy to change in outcome measures.

In order to compare the effectiveness of the assigned interventions in controlling sleep apnea over the course of the study, an additional exploratory analysis will compare the change in AHI, change in time in periodic breathing, and change in time at SpO₂ <90% between the baseline and final portable sleep monitoring studies. This analysis will utilize a one-factor analysis of variance. Further exploratory analyses will assess the relation of effectiveness of control of sleep apnea to changes in the primary outcome measures.

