1). We have used effect estimates based on the meta-analyzed mean effect sizes for CPAP and NSO included in the AASM Practice Parameters paper (41) of 6.4%, and 5.0% for CPAP and NSO, respectively, and an estimated SD of change in LVEF of 4.8% based on previous reports of the effect of either ASV, CPAP or NSO (40, 42, 45-47) on LVEF in patients with sleep apnea. We use the Bonferroni method to account for 2 main comparisons and perform the test comparing each treatment to control at a 2.5% significance level. Using a two-sided two-sample t-test, an evaluable sample size of 34 in the NSO (or CPAP) group and 17 in the HLSE group will achieve 90% power to detect a difference of 5.0% with a significance level of 2.5% assuming a standard deviation of 4.8% in each group, and 98% power to detect a difference in LVEF of 6.4%; there will be 80% power to detect a difference as small as 4.4% between either active treatment group and the HLSE group.

Changes in peak V02 (Aim 2) will be compared in a similar fashion as changes in LVEF. An evaluable sample size of 34 in CPAP or NSO group and 17 in HLSE group will have 80% power to detect a difference of 0.92 standard deviations with a significance level of 2.5% using a two-sided two-sample t-test. Only one study of treatment of central sleep apnea in HF reports the SD of change in peak VO₂, which was 2.5 ml/kg/min (58). The reported change in peak VO₂ with treatment of central sleep apnea with NSO was 1.4-5 ml/kg/min, with a median of 2.5 ml/kg/min (47, 50, 55, 58). The power for this Aim therefore appears adequate.

For the exploratory comparison of CPAP and NSO, the sample sizes of 34 evaluable subjects per group will provide 80% power to detect a difference of 3.3% in change in LVEF, assuming a SD of change of 4.8% and a two-sided significance level of 5%.

As comparisons for secondary outcomes (Aim 4) are exploratory in nature, they will be performed at 5% significance level without multiple comparison adjustment. For comparisons in a continuous outcome between each treatment group and the control group, an evaluable sample size of 34 in CPAP or NSO group and 17 in HLSE group achieve 80% power to detect a difference of 0.84 standard deviations with a significance level of 5% using a two-sided two-sample t-test.

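### Neither the primary change-score ANOVA nor the supporting ANCOVA adjusts for the baseline value of LVEF or peak VO2, so a modest and nearly free gain in precision is left unused

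*Combined protocol and SAP*

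**What the plan says.** The Statistical analysis section states that the analysis of each primary outcome, LVEF and peak VO2, "will consist of a one-factor analysis of variance comparing the mean changes from baseline in LVEF" (or VO2), with two primary contrasts: CPAP against HLSE and NSO against HLSE. It calls this a simple analysis of variance, "with data transformation or adoption of rank-based inference if approximate normality is not present".

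The same section then plans "analysis of covariance models that employ adjustments for recruitment site, age, sex, sleep apnea severity, comorbid illness, smoking and alcohol use", with the stated aim of possibly improving the efficiency of the treatment effect estimates. Baseline LVEF and baseline peak VO2 are not on that list, and no other section adds them. Secondary outcomes are to be handled in a similar way, so the omission carries over to them.

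Both outcomes are available at both visits: at the final visit "all procedures performed at the baseline visit will be repeated", echocardiography and exercise testing included.

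The Sample size and power section uses "an estimated SD of change in LVEF of 4.8" points and an unadjusted two-sample t-test.

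**The concern.** A change score already uses the baseline value, but it fixes the slope of follow-up on baseline at 1. ANCOVA estimates that slope. Unless the true slope is 1, residual variance falls. A plan that fits covariates for efficiency, yet leaves out the covariate with a built-in link to change, misses its own aim. None of the seven listed covariates stands in for baseline LVEF or peak VO2.

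The precision matters because both primary contrasts rest on the same 17 or so evaluable HLSE patients. With a control group that small, chance imbalance in baseline LVEF is also likely, and a change-score contrast carries part of it into the estimate. The primary model omits the randomisation stratification factor as well.

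**Working it through.** **Inputs from the documents** (Sample size and power, unless noted): 34 evaluable patients per active arm and 17 in HLSE; two-sided 2.5% per contrast; SD of change in LVEF 4.8 points; LVEF differences of 5.0, 4.4 and 6.4 points; SD of change in peak VO2, "which was 2.5 ml/kg/min"; median reported peak VO2 change 2.5 ml/kg/min. The low end for oxygen in the Background section ("cardiopulmonary exercise testing of 2.3-5 ml/kg/min") gives a second peak VO2 target of 2.3.

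**Assumed, because the documents give no figure:** correlation r between visits of 0.7 to 0.9, and equal SDs at the two visits. With change SD 4.8, the implied baseline LVEF SD is 4.8/√(2(1−r)) = 6.2, 7.6 and 10.7 points at r = 0.7, 0.8 and 0.9.

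**Step 1. Reproduce the stated power.** The standard error of the contrast is 4.8 × √(1/34 + 1/17) = 4.8 × 0.297 = 1.426. The normal approximation gives 89.7% at 5.0, 98.8% at 6.4 and 80.1% at 4.4, in line with the plan's 90%, 98% and 80%. Noncentral t with the pooled three-arm error (df = 85 − 3 = 82) gives 88.7%, 98.5% and 78.7%. These last values are the reference below.

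**Step 2. Variance ratio of ANCOVA to change score.** With q = follow-up SD / baseline SD, the ratio is q²(1−r²)/(1+q²−2rq). For q = 1 it reduces to (1+r)/2 = 0.85, 0.90 and 0.95. The LVEF SD of 4.8 becomes 4.43, 4.55 and 4.68.

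**Step 3. Cost of estimating two covariates** (baseline and one two-level stratification factor). The df falls from 82 to 80, and chance correlation with arm inflates the expected contrast variance by 1 + 2/79 = 1.0253. No variance reduction is credited to the stratification factor. Gross figures use df 80; net figures add the inflation.

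| Target | ANOVA | ANCOVA gross, r = 0.7 / 0.8 / 0.9 | ANCOVA net, r = 0.7 / 0.8 / 0.9 |
|---|---|---|---|
| LVEF 5.0 | 88.7% | 93.3 / 91.9 / 90.3% | 92.7 / 91.2 / 89.5% |
| LVEF 4.4 | 78.7% | 85.4 / 83.2 / 80.9% | 84.4 / 82.1 / 79.8% |
| LVEF 6.4 | 98.5% | 99.5 / 99.2 / 98.9% | 99.4 / 99.1 / 98.7% |
| Peak VO2 2.5 | 85.8% | 91.2 / 89.5 / 87.7% | 90.5 / 88.6 / 86.8% |
| Peak VO2 2.3 | 79.1% | 85.7 / 83.4 / 81.2% | 84.7 / 82.4 / 80.2% |

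The LVEF difference detectable with 80% power is 4.46 points for ANOVA. For ANCOVA it is 4.12 to 4.35 gross and 4.17 to 4.41 net.

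**Step 4. Less favourable cases, LVEF 5.0, net.**
- *Narrowed baseline range.* Suppose the LVEF entry limit halves baseline variance (assumed; slope kept at r). The ratio is (1+r)/((1+r)+0.5(1−r)) = 0.919, 0.947 and 0.974, and power is 90.6, 89.6 and 88.7%.
- *Slope of 1* (for example r = 0.8 and q = 1.25). The ratio is 1.00 and power is 87.8%, a loss of about 0.9 points.
- *Small departures from equal SDs.* r = 0.9 with q = 1.05 gives a ratio of 0.986 and 88.3%. r = 0.8 with q = 1.1 gives 0.968 and 88.9%.
- *Break-even.* A net gain needs a variance ratio below about 0.975.

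**Step 5. Simulation check** (20,000 three-arm trials per case, LVEF 5.0, baseline slope and site effect estimated, site allocated at random). ANOVA against ANCOVA: 88.5 and 92.7% at r = 0.7; 88.7 and 91.3% at r = 0.8; 89.1 and 89.8% at r = 0.9; 89.1 and 88.1% at r = 0.8 with q = 1.25. Under the null at r = 0.8 the rejection rates are 2.4 and 2.3%, so the error rate is held.

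**Step 6. Chance imbalance.** The standard error of the baseline LVEF difference is 0.297 × 6.2 = 1.8 points at r = 0.7 and 0.297 × 10.7 = 3.2 points at r = 0.9. An imbalance of one standard error shifts the change-score contrast by (1−r) times that, about 0.55 and 0.32 points. ANCOVA removes this shift.

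**The case against.** The strongest reply is that nothing is wrong with the plan. The change-score ANOVA is valid and unbiased under randomisation, it already uses baseline with a fixed coefficient, and the stated power reproduces. What remains is a choice between two valid estimators. All of that is correct.

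The second objection is that the gain depends on two quantities the documents do not supply, the visit correlation and the ratio of SDs. Step 4 shows that this has force: at r = 0.9 a follow-up SD only 5% larger than baseline turns the gain into a small loss. The dependence runs both ways, though. At r = 0.9 with a follow-up SD 10% smaller than baseline, net power is 93.9%, and at r = 0.5 with equal SDs it is 95.5%. In the cases examined, the trade is a loss of at most about 0.9 points at LVEF 5.0 against a gain of about 4 points at r = 0.7 and equal SDs, or about 6 points at LVEF 4.4.

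The third is that which factor stratified the randomisation is a separate question. It is, and it adds no weight to the case for baseline adjustment. It has to be settled only so that the right factor enters the model.

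**Conclusion.** The point holds as a recommended improvement, not a correction. The reading of the plan is certain: the baseline outcome is in neither model, although it is collected at no extra burden. The size of the benefit is not certain. With r between 0.7 and 0.9 and equal visit SDs, the net gain is 4.0 to 0.8 percentage points at LVEF 5.0, 5.7 to 1.1 at LVEF 4.4, and 4.6 to 0.9 at peak VO2 2.5. At LVEF 6.4, where the plan already claims "98% power to detect a difference in LVEF of 6.4" points, it is below 1 point. At r of 0.7 to 0.8 with equal SDs, net power for LVEF 5.0 and 4.4 exceeds the 90% and 80% the plan states; noncentral t puts the planned ANOVA slightly below both. A slope near 1 removes the gain.

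**What to change.** - Prespecify as primary, for each outcome, an ANCOVA of the 12-week value on arm, the baseline value of the same outcome, and the randomisation stratification factor, with the same two contrasts at 2.5%. With baseline in the model, using change as the response gives the same treatment estimate.
- Keep the change-score ANOVA as a sensitivity analysis, so that the choice of model is fixed in advance.
- Say how the fallback for non-normal data applies to the ANCOVA, for example rank ANCOVA, and how the no-change imputation for drop-outs enters it (12-week value set equal to baseline).
- Add the baseline outcome to the longer covariate model.
- Separately, reconcile the Randomization paragraph, which says allocation is stratified by recruitment site but describes a lookup of the stratum by predominant sleep apnea type. Adjust for the factor actually used.

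The cost is SAP wording and a check of the randomisation lists. No new data are needed. Statistically, the two lost degrees of freedom and the roughly 2.5% variance inflation together take 0.6 to 0.8 points off power at LVEF 5.0, nearly all of it from the inflation. The net figures already include this.

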Ambulatory Blood Pressure Monitoring. Participants will be instructed in the use of an Ambulatory Blood Pressure monitor. The device consists of a blood pressure cuff that is connected by rubber tubing to a small pressure monitoring device that weighs only 9 oz and fits easily in a shirt pocket. The device will be programmed to measure BP at 20 minute intervals during the day and 30 minute intervals at night (11 PM to 7 AM) for the subsequent 24 hours. A pre-paid addressed box will be provided for mail return of the device.

Randomization. After completing testing at the baseline visit, and being instructed in the use of the ambulatory blood pressure monitor, participants will be randomly assigned in a 1:2:2 ratio to one of three treatment groups: **Healthy Lifestyle and Sleep Education** alone (HLSE); HLSE plus Continuous Positive Airway Pressure (CPAP); or HLSE plus nocturnal supplemental oxygen (NSO). Randomization will be performed using permuted blocks, stratified by recruitment site. A SAS program will be used to generate two separate lists of randomization assignments for the two strata. These lists will be

placed into a single data table in a Microsoft SQL Server 2008 database to serve as a lookup table. When a new participant record is created in the database, a trigger is fired on the SQL Server randomization data table that looks up the corresponding stratum using predominant sleep apnea type, picks the next assignment from that stratum, updates the lookup table with the Study ID randomized and the date/time of randomization. Due to the nature of the treatments, blinding of subjects to treatment arm is not possible. The ultrasonographers and physicians overseeing and scoring the echocardiograms and cardiopulmonary exercise tests will be blind to treatment assignment.

Treatment

Healthy Lifestyle and Sleep Education (HLSE Group)

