identifiers. Only study personnel will have access to research data, which is kept either in locked cabinets, in password-protected computers in locked offices, or on secure password-protected drives located behind the VA firewall or at the Center for Clinical Investigation at Brigham & Women's Hospital. All personal data will be stored separately from de-identified research data, and will be stored in password-protected files behind the VA firewall or in locked cabinets within the VA. Blood and specimens will be stored using de-identified bar codes at the VA Boston and shipped to [name] laboratory, the VA Boston clinical lab for testing. Once the assays have been run on the samples, any leftovers will be destroyed.

Risks from cardiopulmonary exercise testing will be minimized by close physician supervision of testing, which will be performed by trained technicians in the Cardiopulmonary Exercise Laboratories at the VA Boston and VA Connecticut HCS sites, with emergency equipment readily available. Although patients will be encouraged to exercise to their symptomatic limits, if there are any signs of medical instability, the cardiologist will end the test before the symptomatic endpoint is achieved.

Phlebotomy will be performed by trained phlebotomists.

All CPAP devices will be equipped with heated humidifiers to minimize drying, and attention will be paid at set-up to identifying a best-fit mask to minimize mask discomfort and air leaks. Subjects will be contacted at weeks 1, 2, 4 and 8 to identify any early problems with treatment and to ascertain any adverse events, in particular the onset of dangerous levels of sleepiness. Participants will be extensively counseled at the baseline visit on safety measures related to excessive sleepiness. Participants randomized to NSO will be counseled on risks of fire from use of oxygen near open flames, including cigarettes.

Potential Benefits of the proposed Research to Human Subjects and Others

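### The primary ANOVA omits the randomisation's stratification factor, so its tests are somewhat conservative if mean change differs between strata; the protocol also contradicts itself on which factor that is.

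*Combined protocol and SAP*

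**What the plan says.** The Randomization paragraph (Baseline visit) reads "Randomization will be performed using permuted blocks, stratified by recruitment site" and describes "two separate lists of randomization assignments for the two strata". Two sentences later, the database trigger "looks up the corresponding stratum using predominant sleep apnea type". The stated factor and the look-up factor are therefore different.

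Under Statistical analysis, the model for each primary outcome "will consist of a one-factor analysis of variance comparing the mean changes from baseline in LVEF" (or peak VO2). The plan names "CPAP vs. HLSE and NSO vs. HLSE as our primary analyses" and then describes the model again: "This analysis is a simple analysis of variance, with data transformation or adoption of rank-based inference if approximate normality is not present". Site is not in it.

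The same paragraph adds "analysis of covariance models that employ adjustments for recruitment site", age, sex, sleep apnea severity, comorbid illness, smoking and alcohol use. The stated aim is better efficiency. These models are not called primary, and no rule says what follows if they disagree with the ANOVA. Sleep apnea type is not on the covariate list.

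**The concern.** Blocking within strata keeps the arms close to balanced in each stratum, so a difference in mean change between strata largely cancels from the treatment contrasts. A treatment-only ANOVA does not use this: variation between strata stays in its residual. If such a difference exists, the reported standard error exceeds the true one, the 97.5% intervals are somewhat wide, and each test rejects less often than 2.5% under the null.

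What is at stake is precision in the analysis that decides the trial, with 17 evaluable controls planned. A site difference in change is possible: exercise tests are run in the "Cardiopulmonary Exercise Laboratories at the VA Boston and VA Connecticut HCS sites" (Protection against risks). The documents do not show that one exists.

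**Working it through.** **Inputs.** From Sample size and power: 34 evaluable patients per active arm, 17 in HLSE, SD of change in LVEF 4.8 points, two-sided alpha 0.025 per contrast, differences of 5.0, 6.4 and 4.4 points. Assumed, because the documents do not give them: two strata of equal size, arms balanced within each, and a difference in mean change between strata of D within-stratum SDs.

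**The plan's own figures.** k = √(1/34 + 1/17) = 0.2970, so the standard error is 4.8 × 0.2970 = 1.426. The normal approximation Φ(δ/1.426 − 2.241) gives 89.7%, 98.8% and 80.1% for 5.0, 6.4 and 4.4 points, against the stated 90%, 98% and 80%, so the stated power reproduces. With the noncentral t and the three-arm pooled error (85 − 3 = 82 df) it is 88.7%, 98.5% and 78.7%. That is the baseline for what follows.

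**Variance left in the residual.** With equal strata, the unadjusted error variance is the within-stratum variance times f = 1 + D²/4. If 4.8 is the total SD, the within-stratum SD is s = 4.8/√f.

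**True alpha without the stratum term.** 2·P(T₈₂ > 2.283·√f), treating the residual as scaled chi-square with 82 df.

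**Power.** The noncentrality is δ/(s·k). Without the stratum the critical value is 2.283·√f on 82 df; with it, 2.284 on 81 df.

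| D | Stratum difference (LVEF points) | f | True alpha without | Power at 5.0: without / with | Power at 4.4: without / with |
|---|---|---|---|---|---|
| 0 | 0 | 1 | 2.5% | 88.71 / 88.70 | 78.73 / 78.71 |
| 0.25 | 1.2 | 1.016 | 2.4% | 88.9 / 89.2 | 78.9 / 79.4 |
| 0.5 | 2.3 | 1.063 | 2.1% | 89.4 / 90.6 | 79.4 / 81.3 |
| 0.75 | 3.4 | 1.141 | 1.7% | 90.2 / 92.6 | 80.2 / 84.2 |

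The gain from adding the stratum is about 0.3, 1.2 and 2.4 points at 5.0, and 0.5, 1.9 and 4.0 points at 4.4. The standard error is overstated by √f − 1: 0.8%, 3.1% and 6.8%.

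**Sensitivity to the meaning of 4.8.** If 4.8 is instead the within-stratum SD, s stays at 4.8 and unadjusted power falls as D grows. At 4.4 points it is 76.7% against 78.7% with the stratum for D = 0.5, and 74.0% against 78.7% for D = 0.75.

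**Simulation check.** 85 patients were simulated in permuted blocks of 5 within two equal sites, with within-site SD 4.8 (12,000 runs per null setting). With site differences of 2 and 4 points, null rejection was 2.0% and 1.6% without site, and 2.3% and 2.5% with it. The mean model standard error without site was 1.454 and 1.543, against true values of 1.421 and 1.426. A 70:30 split showed the same pattern (2.4% and 1.5% without site).

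**The case against.** The strongest reply is that the primary test is valid and errs only on the cautious side, that the effect is small unless strata differ a good deal, and that a site-adjusted ANCOVA is already planned. Most of this stands. D = 0.5 means about 2.3 LVEF points between sites, roughly the whole CPAP effect of 2.2% that the Background quotes from the multicentre trial. The outcome is within-patient change, so a stable laboratory or reader offset cancels. The protocol also specifies one ultrasound model, one LVEF method and blinded scoring. The planned ANCOVA does not settle the matter, however, because it is not the analysis on which the conclusion rests.

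Three stronger readings are tempting and not supported:

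- A reader might infer that planned power is lost. With 4.8 as the total SD, unadjusted power never falls below its no-difference value (88.7% at 5.0 points, 78.7% at 4.4). What is forgone is a gain. An absolute loss appears only if 4.8 is the within-stratum SD; the plan describes it simply as the SD in each group.
- A reader might infer that stratifying achieves nothing under this analysis. It still balances the factor across arms and reduces the true variance of the contrasts.
- A reader might infer that each site performs its own echocardiograms. The Echocardiogram section does not say where they are done or read; only the exercise laboratories are placed at both sites.

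The look-up sentence also limits the argument about site. If assignment ran by apnea type, site was not balanced by design and the unadjusted test has about the right alpha with respect to site. The same reasoning then applies to apnea type, which neither model contains.

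**Conclusion.** The point holds as one of efficiency and consistency. The primary model leaves out the factor by which the protocol says it randomises. Where mean change differs between strata, the tests are mildly conservative: true alpha 2.4% to 1.7% for D from 0.25 to 0.75, with 0.3 to 2.4 points of power available at a 5.0-point difference and 0.5 to 4.0 at 4.4. Where it does not differ, there is no harm either way.

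These sizes rest on equal strata, 4.8 as the total SD, and an assumed D; the documents supply neither a between-site difference nor a site split. There is no inflation of type I error and no bias. The contradiction in the Randomization paragraph does not depend on any of these assumptions and has to be resolved first, because it decides which factor belongs in the model.

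**What to change.** 1. In the Randomization paragraph, state which factor the two lists and the database look-up actually used, and make the sentences agree.
2. Under Statistical analysis, define the primary model for LVEF and for peak VO2 as change on treatment arm plus that factor, and take the CPAP vs HLSE and NSO vs HLSE contrasts from it.
3. If rank-based inference is adopted, specify a version stratified by the same factor.
4. Keep the wider ANCOVA as supplementary.

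The cost is a few sentences and one error degree of freedom (82 to 81), or about 0.01 to 0.02 points of power if the strata do not differ. Site is already on the planned covariate list, and apnea type is what the look-up reads, so no new data should be needed. The change should be made before outcome data are examined by arm.
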